7.1. Study Subjects

7.1.1. Disposition of Subjects

Enrolled patients (Full Analysis Set) will be summarized using frequencies and percentages from the screened population.

Protocol deviations will be summarized and listed, and per-protocol patients will be summarized (frequency and percentage from Full Analysis Set population).

Frequency and percentage of FAS patients with full follow-up will be reported, as well as patients with early withdrawal from the study, and the related reasons. Please refer to section 7.1.3

7.1.2. Clinical Investigation Plan (CIP) Deviations

Any deviation from specified statistical plan will be in addition to “per protocol” analysis and will be reported as such. Post-hoc analysis will be conducted according to the existing data gathered, if necessary.

Full-list of protocol deviations will be provided in a separate file; protocol deviations to be excluded from PPAS1 and PPAS2 (refer to section 7.1.3) will be discussed and validated with the study team prior to run statistical analysis.

7.1.3. Analysis Sets

Two analysis sets will be created for study purpose:

1. Full Analysis Set (FAS). FAS includes all enrolled subjects:

- who signed the informed consent and
- who satisfied to the eligibility criteria

FAS will be used for subjects disposition, population description, and for Safety analysis.

2. Per Protocol Analysis set (PPAS): PPAS is a subset of the FAS, restricted to subjects who adhere to the protocol, in terms of SPM and Scintigraphy procedures, and minimal follow-up.

Two subsets of the PPAS - according to follow-up- will be created and used for Performance analysis purpose:

- PPAS1: Subjects who completed the full study follow up to 6 months FU
- PPAS2: Subjects who completed visit 4 with 3 patient management plans- this group will be larger than the above and will have all data for study end points, even though not completed full study flow.

Listing of major protocol deviations to be excluded from the PPAS1 and 2 will be provided by the study team prior to run statistical analysis.

Per protocol Analysis Sets (PPAS1 and PPAS2) will be used for Performance analyses.

7.2. General Methodology

Continuous variables will be summarized using tables of descriptive statistics: number of patients with recorded observations, mean, standard deviation, median, minimum and maximum. Categorical variables will be summarized using counts and percentages. Descriptive statistics will be presented by diagnosis and clinical center. Diagnostic outcome will be tabulated and compared for SPM and conventional test and percentage gain determined. Frequency of patient management change resulting from SPM test relative to conventional test will be recorded for categories of: therapy, elimination of diagnostic testing, diet and surgery.

Statistical analysis will consist in:

- Descriptive analysis of patients characteristics and assessments before and after study procedures.
- Agreement analyses between SmartPill Motility Monitoring System and Gastric Scintigraphy (GS)
- Correlation analysis between PAGI-SYM, PAGI-QOL and SPM and GES.
- Descriptive and Comparative analysis of safety parameters related to procedures, between SPM and GES.

Parameters ascribed to the safety of patients will be summarized by diagnosis and clinical center.

All available data from patients who fail to complete this study will be included in all safety summaries.

Agreement analysis (primary and secondary endpoints) will be run to provide % of agreement (overall, positive and negative agreement) between both procedures, as well as Kappa coefficient, p-value and 95% confidence interval.

Correlation analysis (between two quantitative parameters) will be run: Pearson coefficient, p-value and 95% confidence interval will be calculated.

For other analyses:

- Continuous variables will be summarized using descriptive statistics, specifically the mean, standard deviation, median, minimum and maximum. Comparison of continuous parameters between two groups will be performed using T-test or Wilcoxon Man-Whitney U test, or Wilcoxon signed rank test (non-parametric) for paired data, as appropriate.
- Categorical variables will be summarized using frequencies and percentages, and compared between two groups using Chi-Square or Fisher exact test, or Mac Nemar Chi-square test for paired data, as appropriate.

Subject disposition and follow-up, as well as demographic and baseline characteristics of patients, results related to SPM and GES , or to any questionnaire will be described for each clinical center.

Reporting outputs

All outputs will be produced using SAS® version 9.4 and Minitab v15.0.

Tables and listings will be produced as PDF files and Courier New font size 9 bold.

Outputs will be ordered in the order that they appear in the textual sections of the plan i.e. disposition outputs first, followed by protocol deviations, baseline outputs, compliance outputs, effectiveness outputs and safety outputs.

The listings will be ordered by site, subject and visit as applicable, unless otherwise stated.

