2. To assess the correlation of gastroparetic symptoms measured by the PAGI-SYM symptom survey and PAGI-QUL survey instruments with SPM transit and fed response contractility parameters and with gastric emptying scintigraphy. *Hypothesis:* Gastroparetic symptoms correlate with discrete SPM measures
3. To quantify the additional abnormal motility (diagnostic gain) detected with SPM relative to GES. *Hypothesis:* The GI transit and contractility measures provided with SPM result in additional abnormal motility findings (diagnostic gain) over the conventional test gastric emptying scintigraphy in the symptomatic gastroparetic population
4. To assess the impact of the diagnostic gain associated with SPM on patient management
Hypothesis: The diagnostic gain realized with SPM results impact patient management decisions.

Study Endpoints

1. Primary Endpoint

Per patient device agreement for the diagnosis of delayed gastric emptying between SmartPill Motility Monitoring System (SPM) gastric emptying time (GET >5 hours) (18) and

the non-reference standard, gastric Emptying scintigraphy test (>10% retention of a solid meal at 4 hours)(13) in patients with symptoms of gastroparesis

2. Secondary Endpoints

2.1. Agreement between Gastric emptying time of smartpill capsule (GET>8hrs= severe) and gastroduodenal contractility and percent of radiolabeled meal retained at 4 hours on scintigraphy (>35% = severe)

2.2. Correlation between total GCSI scores, GCSI subscale scores for nausea/vomiting, postprandial fullness/early satiety, bloating , PAGA-SYM score for upper abdominal pain, PAGA-QOL score and SPM GET, SPM SBTT, SPM CTT, SPM fed response gastroduodenal contractility (frequency and AUC) and percent retention of radiolabeled meal measured with scintigraphic camera at 4 hours,

2.3. Number of abnormal SPM GET, SBTT,CTT and antroduodenal contractility findings (contraction frequency and AUC) and number of abnormal radiolabeled meal emptying findings measured with scintigraphic camera.

2.4. Documented patient management plans recording therapy, Dx tests, nutrition, and surgery decisions based on SPM results and based on GES and assessment of patient management change in accordance with following guidelines:

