a. Change in Therapy: A change in category of drug therapy or the addition of a new category of drug therapy constitutes a change in management. Thus a change in treatment from prokinetic to antiemetic, neuromodulator or laxative category constitutes a change in patient management. A change of therapy within category such as switching from one prokinetic drug to another prokinetic drug does not constitute a change in patient management unless the drug is intended to impact a different GI region.

b. Dietary guidelines: Changes to diet constituting a change in patient management include: recommendation of diets specific for gastroparesis, recommendation of a liquid diet, initiation of TPN or G or J feeding tube.

c. Surgery: Relocation of feeding tube to new location (G tube changed to J Tube) constitutes change in management but not relocation of G tube to new gastric location. Either initiation or elimination of surgical referral constitutes change in management.

d. Diagnostic Testing: Any avoidance or additional diagnostic testing related to patient GI symptoms whether to detect abnormal motility or rule out alarm conditions constitute a change in management.

5. Investigation Plan

This is a multi-center, prospective study which aims to evaluate positive and negative device agreement in the diagnosis of delayed gastric emptying between SPM system gastric emptying time (GET >5 hours) and the non-reference standard gastric emptying scintigraphy test (>10% retention of a solid meal at 4 hours) in patients with symptoms of gastroparesis.

The study will include approximately 275 patients with symptoms of gastroparesis aged 18-80 years, who have no evidence of metabolic and/or organic disease.

Each subject will go through a Gastric scintigraphy test concurrently conducted with SPM testing after an overnight fast. The subject will be instructed to maintain a diary of times of meal consumption, bowel movements, and sleep.

Patient and physician will complete survey instruments (detailed in section 7 of protocol).

Subject will return the SPM receiver 5+2 days after ingestion day.

Physician will complete 4 management plans:

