3. The relative frequency will be computed for SPM transit and contractility results that provide diagnostic gain (additional abnormal motility findings) compared to conventional test results. A corresponding 95 percent confidence interval will also be provided.

4. The percent of changes to patient management plans will be estimated. Frequencies of the types of changes will be summarize and presented in tabular form.

Secondary performance endpoints will be run on both PPAS1 and PPAS2.

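### Section 7.2 records a change in diagnostic testing only when a test is eliminated, whereas endpoint 2.4(d) also counts tests added

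*SAP*

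**What the plan says.** Endpoint 2.4 (section 4, Secondary Endpoints) rests on "Documented patient management plans recording therapy, Dx tests, nutrition, and surgery decisions based on SPM results" and on the scintigraphy results. It says that change is to be assessed by the four guidelines that follow it. Guideline d, on testing, reads "Any avoidance or additional diagnostic testing related to patient GI symptoms". Guideline c, on surgery, is also two-directional: "Either initiation or elimination of surgical referral constitutes change in management".

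Section 7.2 (General Methodology) says that the frequency of management change resulting from SPM, relative to the conventional test, will be recorded for "categories of: therapy, elimination of diagnostic testing, diet and surgery".

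Section 7.9, secondary analysis 4, says "The percent of changes to patient management plans will be estimated" and that the types of change will be tabulated. It lists no types and refers to neither 2.4 nor 7.2.

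**The concern.** Two places in the SAP describe the same quantity differently. Under the endpoint definition, a patient whose plan gains a test has had a management change. Under the 7.2 list, that patient belongs to no testing category. Of the four 7.2 categories, testing is the only one given a direction.

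Objective 4 asks whether the extra findings from SPM affect management. More abnormal findings may spare some tests and prompt others. A table of eliminated tests alone shows a reader only the saving. It also leaves the analyst free to choose between two written versions, in a SAP that records an interim look and an early stop to enrolment (sections 7.8 and 7.12).

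**Working it through.** The SAP states no rate of management change, so there is no figure of its own to reproduce. The check is a comparison of texts, followed by an illustration.

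**Texts side by side**

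| Place | Test avoided | Test added |
|---|---|---|
| Section 4, endpoint 2.4(d) | counts as change | counts as change |
| Section 7.2 category list | has a category | has no category |
| Section 7.9, secondary analysis 4 | not specified | not specified |

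**What differs.** Let n be the patients analysed, A those with a test avoided, D those with a test added and none avoided, and U the members of D with no change in therapy, diet or surgery.

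- Testing category under 7.2: A/n.
- Testing category under 2.4(d): (A + D)/n.
- Shortfall in the overall rate of 7.9: U/n if 7.2 governs that rate, and 0 if 2.4 governs it. U lies between 0 and D.

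If 7.2 fixes the category table and 2.4 fixes the overall rate, the two outputs do not reconcile. The U patients count as changed overall but appear under no category.

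**Illustration.** Final enrolment is 167 (section 7.12). Section 6 expects 10% of data to be lost or not evaluable. Applying that to 167 gives 0.9 × 167 = 150.3, taken as n = 150. A = 15 and D = 5, 15 or 30 are assumptions with no source in the SAP. Intervals are Clopper-Pearson 95%.

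| D (assumed) | 7.2 category | 2.4(d) category | Overall shortfall if 7.2 governs 7.9 |
|---|---|---|---|
| 5 | 15/150 = 10.0% (5.7 to 16.0) | 20/150 = 13.3% (8.3 to 19.8) | 0 to 5/150 = 0 to 3.3 points |
| 15 | 15/150 = 10.0% (5.7 to 16.0) | 30/150 = 20.0% (13.9 to 27.3) | 0 to 15/150 = 0 to 10 points |
| 30 | 15/150 = 10.0% (5.7 to 16.0) | 45/150 = 30.0% (22.8 to 38.0) | 0 to 30/150 = 0 to 20 points |

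The 7.2 figure does not move with D, so a reader of that table could not tell the three cases apart.

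**The case against.** The strongest reply is that the SAP already defines management change. Endpoint 2.4 ties its assessment to guidelines a to d. Section 7.9, the specific analysis of this endpoint, is unrestricted and fits them. Section 7.2 is general text whose four labels follow the four headings of 2.4, and it does not say that added tests are excluded. On that view the 7.2 wording is a badly chosen label.

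Much of this stands. It is the natural reading for the overall rate, even though the SAP states no order of precedence. The two-directional wording for surgery in 2.4(c) is weak evidence that the 7.2 label was deliberate, because it sets a definition beside a label. The reply does not rescue the 7.2 table itself. That list is the only one in the analysis text, and a programmer who followed it would omit added tests while complying with the plan.

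A reader might also infer that the diagnostic-gain analysis is one-sided in the same way, since 7.9, secondary analysis 3, speaks of "SPM transit and contractility results that provide diagnostic gain (additional abnormal motility findings) compared to conventional test results". The document does not support that:

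- Section 7.2 promises "Diagnostic outcome will be tabulated and compared for SPM and conventional test and percentage gain determined".
- Endpoint 2.3 includes the "number of abnormal radiolabeled meal emptying findings measured with scintigraphic camera".
- The counts behind positive and negative percent agreement in the primary analysis give all four cells of gastric emptying time against scintigraphy.
- Nothing in the SAP prescribes a single pooled gain across all the SPM measures.

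**Conclusion.** The conflict between 7.2 and 2.4(d) is real. The firm defect is confined to the 7.2 category table: produced as written, it shows tests avoided and leaves out tests added. That lowers the count of testing changes and keeps only the direction that reads as a saving from the device.

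A reader might go further and conclude that the overall rate of management change will be understated. That follows only if 7.2 is taken to govern 7.9, which the SAP does not say and endpoint 2.4 speaks against. Nor does the wording imply lost data, because the management plans record testing decisions.

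The size cannot be known from the SAP. The percentages above rest on assumed counts and show only the form of the effect. The endpoint is descriptive and secondary, and the primary agreement analysis is untouched. The point is minor to moderate, and worth correcting because the correction is so small.

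**What to change.** In section 7.2, replace the single testing category with two, diagnostic testing avoided and diagnostic testing added, and tabulate them separately. A patient may have both, so the two rows need not sum to the number with any testing change. In section 7.9, secondary analysis 4, state that changes are counted by guidelines 2.4 a to d.

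The cost is one phrase and one cross-reference. The testing decisions are already recorded in the management plans, so the SAP points to no new data collection. The price to the sponsor is that the testing result may look less favourable once added tests stand beside those avoided.

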7.3. Center Pooling

Descriptive statistics will be presented by diagnosis and clinical center. Parameters ascribed to the safety of patients will be summarized by diagnosis and clinical center.

7.4. Handling of Missing Data and Dropouts

No method of imputation will be used for missing data. A summary of missing data will be provided according to the number of subjects, the time points where the data are missing and

clinical center. For each clinical center, number and percent of subjects with no missing data will be presented in tabular form.

7.5. Adjustments for Multiple Comparisons

No adjustment will be made.

7.6. Demographic and Other Baseline Characteristics

Patient's characteristics and other baseline data will be summarized and reported using statistical methods described above (see section 7.2 General Methodology).

7.7. Treatment Characteristics

Scintigraphy procedure and SPM procedure completions will be evaluated; all event or technical failure occurring during procedures will be described and reported in data-listing.

Patients with medications (Y/N) will be summarized at baseline and at each follow-up ; details on medications will be provided using data-Listing, for each visit.

7.8. Interim Analyses

One (partial) interim analysis Interim analyses has already been performed (June 2015) on primary endpoint, on N=130 patients. Final analysis will occur on 167 enrolled at the end of the study.

7.9. Evaluation of Objectives

III.2 Primary analysis

Since a clearly defined universally accepted physiological definition of disease in this population does not exist, the diagnostic test under evaluation (SPM GET) will be compared to a non-reference standard test method, the percent retention of a radiolabelled solid meal at 4 hours on gastric scintiscanning. Device agreement will be examined through use of the positive percent agreement (PPA) and negative percent agreement (NPA). (38), the Statistical Evaluation of

Medical Tests for Classification and Prediction. Oxford University Press Inc, New York. Let π_{PPA} represent the true positive percent agreement defined as the probability of a positive SPM test result given the non-reference is positive and let π_{NPA} represent the probability of a negative SPM test result given the non-reference is negative. The primary analyses of this trial is estimation of these parameters in order to assess the equivalence between the diagnostic test under evaluation and the non-reference standard. Maximum likelihood estimates of π_{PPA} and π_{NPA} will be computed based on collected data i.e., conditional relative frequencies in addition to corresponding 95% confidence intervals based on the methodology of Clopper and Pearson (28). Additional measures such as estimates of the overall percent agreement and Cohen's kappa will be calculated.

Primary endpoint analysis will be run on PPAS1 and PPAS2.

III.2 Secondary analyses

1. The correlation between diagnoses of profound gastric retention on scintigraphy (>35% at 4 hours) with severe prolongation of SPM GET (>8 hours) and impaired contractility will be examined using relative frequencies. 95% confidence intervals will also be provided.
2. Total GCSI scores as well as GCSI nausea/vomiting, GCSI postprandial fullness/early satiety, and GCSI bloating subscale scores, PAGI-SYM upper abdominal pain scores and PAGI-QOL scores will be correlated with SPM GET, SPM SBTT, SPM CTT scintigraphy gastric retention at 4 hours and SPM gastroduodenal and fed response contractility profiles. Since validity of the standard confidence interval corresponding to the Pearson correlation requires distributional assumption which will not be met based on the nature of the data to be collected, bootstrap methodologies will be utilized alternatively to construct said intervals.
3. The relative frequency will be computed for SPM transit and contractility results that provide diagnostic gain (additional abnormal motility findings) compared to conventional test results. A corresponding 95 percent confidence interval will also be provided.

4. The percent of changes to patient management plans will be estimated. Frequencies of the types of changes will be summarize and presented in tabular form.

Secondary performance endpoints will be run on both PPAS1 and PPAS2.

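### The primary agreement analysis is run only on sets that require post-test follow-up, and neither set is named primary

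*SAP*

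**What the plan says.** Section 4 sets the primary endpoint as "Per patient device agreement for the diagnosis of delayed gastric emptying" between SPM (gastric emptying time above 5 hours) and scintigraphy (more than 10% of the meal retained at 4 hours). Section 7.9 defines PPA as "the probability of a positive SPM test result given the non-reference is positive", with NPA as its counterpart among scintigraphy-negatives. Both come with 95% Clopper-Pearson intervals.

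The sets are fixed in 7.1.3. The per-protocol set is "restricted to subjects who adhere to the protocol, in terms of SPM and Scintigraphy procedures, and minimal follow-up". It splits into two:

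- "PPAS1: Subjects who completed the full study follow up to 6 months FU"
- "PPAS2: Subjects who completed visit 4 with 3 patient management plans", of which the SAP adds that "this group will be larger than the above and will have all data for study end points"

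The full analysis set has other uses: "FAS will be used for subjects disposition, population description, and for Safety analysis". Section 7.9 then says "Primary endpoint analysis will be run on PPAS1 and PPAS2", without ranking them or saying what happens if they differ. Section 7.4 rules out imputation.

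**The concern.** By the definitions in 7.9, PPA and NPA use two classifications per patient and nothing else. Section 5 has both tests conducted concurrently. The management plans at visit 4 are written from the test results, and the contacts at 3 and 6 months assess symptoms. None of these later steps feeds the primary estimate, yet entry to either set depends on them.

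Two things are at stake. First, patients with complete primary data are left out. If leaving is unrelated to whether the two tests agreed, this costs only precision. If it is related, PPA and NPA are biased. The plausible route concerns PPAS1: the plan based on both results is presented to the patient at visit 4 and may influence who stays to 6 months. That route does not explain missing visit 4 itself, and the SAP suggests no specific bias route for PPAS2.

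Second, the trial has no defined headline result. The analysis is estimation without a success threshold, so the problem is an undefined primary estimate and not an inflated error rate.

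**Working it through.** **What each analysis needs and requires**

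| | SPM and scintigraphy results | Visit 4 with three plans | Follow-up to 6 months |
|---|---|---|---|
| Needed for PPA and NPA (7.9) | yes | no | no |
| Required for PPAS2 (7.1.3) | yes | yes | no |
| Required for PPAS1 (7.1.3) | yes | part of full follow-up | yes |

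No set has only the first column as its condition. By the SAP's own account PPAS2 already holds all endpoint data, so the 6-month condition in PPAS1 removes patients whose primary data are complete.

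**Inputs.** 275 planned, 10% lost to follow-up or not evaluable, 40% scintigraphy-positive (section 6); 167 enrolled at the end (7.8, 7.12); Clopper-Pearson intervals (7.9). The loss patterns by concordance below are assumptions.

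**The plan's own figures.** 275 × 0.90 = 247.5, the stated 248. 0.40 × 248 = 99 positives. The normal-approximation half-width at 50% is 1.96 × √(0.25/99) = 9.8 points, the stated maximum. The expected Clopper-Pearson half-width at n = 99 is 10.2.

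**Precision at 167 enrolled.** Expected half-width = Σ over x of Binomial(x; n, p) × (upper − lower)/2, with p = 0.5.

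| | n | Half-width (points) |
|---|---|---|
| PPA, nobody lost: 167 × 0.40 = 66.8 | 67 | 12.39 |
| PPA, 5% not evaluable: 66.8 × 0.95 = 63.5 | 63 | 12.78 |
| PPA, full 10% lost: 66.8 × 0.90 = 60.1 | 60 | 13.09 |
| NPA, nobody lost: 167 × 0.60 = 100.2 | 100 | 10.12 |
| NPA, full 10% lost: 100.2 × 0.90 = 90.2 | 90 | 10.67 |

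The 10% also covers tests that cannot be evaluated, which no choice of set recovers. If all of it is follow-up loss, the avoidable cost for PPA is 13.09 − 12.39 = 0.70 points. If half is, it is 13.09 − 12.78 = 0.31. If none is, it is zero.

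**Bias at a true PPA of 70%, total loss 10%.** Let discordant patients be lost r times as often as concordant ones. The concordant loss is l = 0.10/(0.70 + 0.30r), and the PPA read from those who remain is 0.70 × (1 − l)/0.90.

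- r = 2: l = 0.10/1.30 = 0.0769; retention 92.3% concordant, 84.6% discordant; PPA reads 71.8%.
- r = 1: l = 0.10; PPA reads 70.0%.
- r = 0.5: l = 0.10/0.85 = 0.1176; retention 88.2% concordant, 94.1% discordant; PPA reads 68.6%.
- Arithmetic limits: 0.70/0.90 = 77.8% if every loss is discordant, 0.60/0.90 = 66.7% if every loss is concordant.

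A larger shift at less extreme patterns needs more loss than the SAP expects. Retention of 90% and 75% gives 0.63/(0.63 + 0.225) = 73.7%, but that is a total loss of 14.5%.

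**The case against.** The strongest reply is that the effect is small and may be nil.

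- **PPAS2 is a light condition.** It asks for one visit 5 to 28 days after the tests. The SPM receiver comes back at 5+2 days, so patients lost early may lack SPM data anyway. This stands as a point about size: the number with both results who miss visit 4 could be zero. It gives no reason to make visit 4 a condition.
- **Running both sets is a check.** A distortion from 6-month attrition would show as a difference between PPAS1 and PPAS2. That is fair for PPAS1. The comparison cannot show the effect of omitting patients who miss visit 4, because they are in neither set, and a sensitivity comparison still needs a named primary.
- **The shifts are modest.** Changes of +1.8 or −1.4 points compare with an expected half-width of 11.4 to 12.1 at a true 70%. The pooled 10% measures neither visit-4 nor 6-month attrition. Both remarks are correct, which is why the figures are illustrations only.
- **Disposition is already reported.** Section 7.1.1 gives per-protocol counts and withdrawal reasons, 7.4 a missing-data summary and 7.7 procedure completion. What remains missing is narrow: the count of patients with both results who are outside each set.
- **A set named now is a choice made after the interim.** Enrolment stopped on interim primary results (7.12). This calls for disclosure; leaving the headline open until reporting would be worse.

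**Conclusion.** The concern holds and should be fixed. The SAP's stated rule omits patients with complete primary data from every agreement analysis and leaves two primary estimates unranked. The lack of a ranking stands whatever the dropout. The numerical harm is modest and unknown in direction: at most 0.7 points of half-width for PPA and just under 0.6 for NPA, and a shift of one to two points in PPA under the two-to-one loss patterns shown. It would be no bias at all if completion is unrelated to concordance. These sizes assume 40% scintigraphy-positive among 167 enrolled and a loss of 10%; the SAP gives no count of the patients concerned.

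**What to change.** In 7.1.3 and 7.9, name one primary agreement set: FAS subjects with both tests classifiable at the SAP's own cut-offs (emptying time above 5 hours; more than 10% retained at 4 hours) and no major SPM or scintigraphy procedure deviation, regardless of visit 4, management plans or 6-month completion. This keeps the procedure part of the per-protocol definition and drops only the follow-up part.

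Label PPAS2 and PPAS1 as supportive. Add to the disposition tables in 7.1.1 the number of subjects with both results whom each set omits. Note in 7.12 that the primary set was named after the June 2015 interim.

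As a minor safeguard, settle the procedure-deviation exclusions without sight of the paired results as far as possible; this is only partly achievable for the 130 patients in the interim.

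The cost is SAP wording and one more run of the same tables. No new data are needed.

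### Secondary objective 4 is about the impact of SPM's diagnostic gain on management, but the planned frequencies of plan change are never related to gain and carry no confidence interval

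*SAP*

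**What the plan says.** Section 4 states secondary objective 4 as "To assess the impact of the diagnostic gain associated with SPM on patient management", with the hypothesis "The diagnostic gain realized with SPM results impact patient management decisions". Endpoint 2.4 in the same section takes documented plans based on SPM and on scintigraphy (GES), and calls for "assessment of patient management change in accordance with following guidelines". The guidelines that follow do not mention gain.

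Section 7.9, secondary analyses, treats gain and change as separate items:
- Item 3 (gain): "The relative frequency will be computed for SPM transit and contractility results that provide diagnostic gain (additional abnormal motility findings) compared to conventional test results", with a 95% interval.
- Item 4 (change): "The percent of changes to patient management plans will be estimated", followed by "Frequencies of the types of changes will be summarize and presented in tabular form". No interval is given.

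Section 7.2 keeps the same separation. On gain: "Diagnostic outcome will be tabulated and compared for SPM and conventional test and percentage gain determined". On change: "Frequency of patient management change resulting from SPM test relative to conventional test will be recorded for categories of: therapy, elimination of diagnostic testing, diet" (the list closes with a surgical category). It also lists chi-square, Fisher and McNemar tests for categorical variables in general, but assigns none of them to this question.

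**The concern.** The exposure named in objective 4 is the gain, not having had an SPM test. Gain and plan change are both known for each patient, yet no planned table, stratification or test puts them together.

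The SAP's own rules allow change without gain. Endpoint 2.4 counts avoided as well as added diagnostic tests, and dropped as well as new surgical referrals. A normal SPM in a patient with abnormal scintigraphy can therefore produce a counted change although SPM found nothing additional. Section 5 also has the second plan written with the first test result known, so two plans may differ for reasons unrelated to gain. Such changes raise the item 4 percentage. Patients with gain and no change enter the denominator of item 4 and the numerator of item 3, but their joint status is not shown.

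At stake is how a secondary objective is read. A high percentage of changed plans could be reported under objective 4 as though it spoke to gain.

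**Working it through.** The SAP gives no rate, effect or sample size for objective 4, so there is no figure of its own to reproduce. Two checks follow. Every gain and change rate in them is an assumption.

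**1. What the two planned percentages determine.** Let g be the proportion with gain, c the proportion with a plan change, and a the proportion with both. The quantity of interest is

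D = a/g − (c − a)/(1 − g),

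and g and c limit a only to the range from max(0, g + c − 1) to min(g, c).

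| g | c | range of a | range of D (points) |
|---|---|---|---|
| 0.5 | 0.5 | 0 to 0.5 | −100 to +100 |
| 0.5 | 0.3 | 0 to 0.3 | −60 to +60 |
| 0.3 | 0.5 | 0 to 0.3 | −71 to +71 |
| 0.3 | 0.3 | 0 to 0.3 | −43 to +100 |

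The ends are algebraic limits, not forecasts, but moderate cases make the same point. Take 150 patients, 75 with gain and 75 with a changed plan. Changes in 50 of 75 with gain and 25 of 75 without (67% vs 33%), or in 25 of 75 and 50 of 75 (33% vs 67%), give identical planned output: 50% gain and 50% change.

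**2. What a cross-tabulation could deliver.** Inputs: 167 enrolled at final analysis (section 7.12) and 10% lost or not evaluable (section 6, stated there for the planned 275 and carried over here as an assumption). 167 × 0.9 = 150.3, about 150. The 95% half width of the difference is

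1.96 × √[p₁(1 − p₁)/n₁ + p₂(1 − p₂)/n₂].

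With 50% change in both groups:
- 75/75: 1.96 × √(0.25/75 + 0.25/75) = 16.0 points
- 45/105: 1.96 × √(0.25/45 + 0.25/105) = 17.5 points
- 120/30: 1.96 × √(0.25/120 + 0.25/30) = 20.0 points

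At 75/75 with 70% vs 30% change it is 1.96 × √(2 × 0.21/75) = 14.7 points. For comparison, the overall percent of changes at 50% of 150 has a Clopper-Pearson interval of 41.7% to 58.3%, a half width of 8.3 points.

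Power (two-sided 5%, normal approximation, N = 150, 30% to 50% with gain) is 0.62 to 0.69 for 60% vs 40% change and 0.93 to 0.97 for 70% vs 40%. The table would be informative for large differences and less so for moderate ones.

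**The case against.** The best reply is that the plan already measures the right thing. Endpoint 2.4 and section 7.2 describe a within-patient contrast of SPM-based and GES-based plans, and item 4 also tabulates change types. The introduction (section 3) presents management impact and diagnostic gain as two parallel aims, which is how items 3 and 4 treat them. On that reading the wording of objective 4 is merely too narrow and could be aligned with the introduction. This part stands: the planned frequencies are a fair description of the impact of SPM overall. It does not rescue objective 4 and its hypothesis as written, since both name the gain. Rewording would close the mismatch by giving up that question, whereas one table keeps it.

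A second objection also has force. Gain versus no gain compares different patients, and those with gain may be sicker or more symptomatic in ways that themselves prompt changes. The no-gain group would include patients with normal SPM and abnormal scintigraphy, where a change is a genuine effect of SPM. The second plan is not blinded to the first test. The difference therefore shows association and should not be the sole criterion for the hypothesis.

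A reader might infer more than the document supports: that an overall percentage is all that is planned, that patients with gain and no change vanish from the results, or that the trial is bound to claim an effect of gain. Types and categories of change are also planned, those patients are counted in both marginal figures, and the SAP sets no test or conclusion rule for item 4.

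**Conclusion.** The point holds in a limited form. As written, the SAP reports how often plans change and how often SPM adds findings, but not whether the two go together. Nothing in that output can support or refute a statement about gain, and item 4 lacks the interval that items 1 to 3 have.

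A reader might go further and conclude that the hypothesis is beyond this trial's reach. The document does not support that: endpoints 2.3 and 2.4 supply both variables for each patient, and section 7.1.3 expects PPAS2 to hold all endpoint data. The gap is in the analysis, not in the data.

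The point concerns one secondary objective and leaves the primary analysis untouched. The link between the mismatch and its consequence rests on the text alone. The precision figures rest on about 150 evaluable patients and the assumed rates. Exclusion of major deviations from PPAS1 and PPAS2 could lower that number.

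**What to change.** In section 7.9, item 4:

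- Report the percent of patients whose SPM-based plan differs from their GES-based plan, with a Clopper-Pearson 95% interval.
- Cross-tabulate this change (yes/no) with diagnostic gain (at least one additional abnormal SPM finding, yes/no) on PPAS1 and PPAS2. Within the no-gain group, show patients with abnormal scintigraphy and normal SPM separately.
- Give the change proportion in each group and their difference, with 95% intervals. State that these are read as association and are not the sole criterion for the hypothesis.
- Limit any statement about gain to this table. The overall percent and the tables by type and category then describe the impact of SPM overall.

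The cost is a few lines of SAP text and one further table per analysis set, with no new data. The downside is precision: under the assumptions above, the difference has a half width of about 16 to 20 points, against about 8 for the overall percent. Specifying the table before the final analysis also avoids having to present it later as post hoc.
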